1. RATIONALE AND INTRODUCTION

Robotic surgery in the pulmonary field: introduction and uses

Robotic surgery is a type of minimally invasive surgery in which the surgeon sits at a console from which, using mechanical arms, he/she controls the instruments inserted into the patient endoscopically [1]. The purpose of this technology is not to replace the surgeon, but to assist him in carrying out increasingly precise operations [2]. Historically, the first uses of robotic surgery date back to the early 1990s and involved abdominal surgery. Currently, in Italy, the greatest use is in the urological sectors, mainly in radical prostatectomy, and in gynecology [3]. However, the use in the thoracic area is spreading rapidly [4]. The use in this area dates back to 2001, when a group from Pisa performed the first lobectomy with the use of the da Vinci® robotic platform in thoracic surgery expanded and the publication of several studies, including a multicenter one, testifies to its development [6]. With regard to pulmonary pathology, it is used both in benign pathology such as bronchiectasis, granulomas and alveolar echinococcus [7], and in the removal of solitary pulmonary nodules, whose nature is to be determined and whose treatment must be minimally invasive. It is also used in diagnosed small cell lung tumors (SCLC) and not (NSCLC) [8]. Moreover, lung metastases and carcinoid tumors were also removed [9].

Epidemiology of lung cancer and indications for surgical treatment

In Europe, lung cancer remains in second place among the most frequent neoplasms in men with 14.2% in 2020, after prostate cancer, while it is in third place with 9.1% in women, after breast cancer and colorectal cancer. Italy reflects the European trend, with 14.1% in men and 7.3% in women [10]. However, in some countries, such as the United Kingdom and Northern Europe, it is now in second place also in women [11]. As regards mortality, lung cancer causes 20.4% of deaths from cancer, remaining the most frequent cause of death from cancer. In fact, five-year survival for lung cancer is still around 18%, respectively 15% for men and 21% for women; this is also due to the high percentage of advanced stage diagnoses [12]. NSCLC represents 80-90% of cases of lung cancer, while SCLC frequency is around 14% [13,14]. As far as Italy is concerned, in 2020 lung cancer was the first cause of cancer mortality in men (23.9%) and the second in women (12.5%) [10]. In the ATS of Milan area in the three-year period 2016-2018, only 23.4% of lung cancers for all ages were diagnosed in stage I and II, and 76.6% in stage III and IV [15]. When the tumor is resectable, and the patient can undergo surgery, the most indicated treatment for this kind of tumor is surgical removal. The National Institute for Clinical Excellence (NICE) recommends to offer surgical treatment to all patients with NSCLC up to stage IIIB. Furthermore, the NICE guidelines suggest lobectomy as a curative intervention when possible, not specifying a preference between the open and the thoracoscopic approach (NICE Guideline 2019). On the contrary, the European Society of Medical Oncology (ESMO) specifies that VATS is the preferable approach in stage I tumors. However, this recommendation has a level of evidence V (studies without control groups, case reports, and expert opinions) and a rating C (insufficient evidence of efficacy).

As regards the structural characteristics, the robotic systems developed so far can have two types of design: a single-arm one for single-access surgery and a multi-arm one for procedures with multiple surgical accesses. Important advantages of the multi-arm system are the ability to cover a larger operating field, to insert and maneuver instruments more easily and to allow for better visibility [16]. Among the 22 developed robotic surgery systems: 13 are still to be refined, 7 are commercialized (da Vinci SI®, da Vinci SP®, da Vinci XI®, da Vinci X®, Freehand v1.2, Surgenius Beta and Senhance[™] Surgical System), 1 is used only for research, and 1 is dedicated only to the transoral and transanal surgical approach [17]. The seven systems currently on the market are manufactured by four companies. Intuitive Surgical is the American company that produces the da Vinci® robots. It was founded in 1995 and represents the world leader in the sector; it has so far launched four generations of robots, of which three are currently on the market. The da Vinci XI® has four robotic arms and enjoys the most advanced instrumentation, the da Vinci X® has the same architecture as the XI, but uses a more economical technology that allows to reduce costs, the da Vinci SP® instead has a single arm architecture. All Intuitive Surgical systems are CE marked and FDA cleared. Surgica Robotica is an Italian company that currently offers the Surgenius Beta system, and it is developing the Surgenius Gamma. Surgenius Beta has the CE mark. TransEnterix is an American company that manufactures the Senhance[™] Surgical System, an FDA-approved and CE-marked three-arm robot. Freehand Ltd is a British company that manufactures Freehand v1.2, a single arm robot with a camera, FDA cleared and CE marked [17].

The platform of the most used robotic system, the da Vinci, consists of several components: the surgeon's console with a three-dimensional vision system and two manipulators, a surgical cart with one or more arms that execute the surgeon's commands, the Endowrist® instrumentation that allows 7 degrees of movement that simulate and amplify the movements of the human hand and wrist, and a visualization system with 3D endoscopes that allows an enlargement of the image in real time. The absence of the tactile function is a significant problem that developers are trying to overcome with the technological innovation of haptic feedback, which allows the surgeon to "feel" the reaction of the tissue or organ to the force exerted [18]. Intuitive surgical, the leading manufacturer of robotic surgery platforms, estimates that over 5 million minimally invasive robotic procedures have been performed since 2000, with nearly 5000 units installed worldwide (https://www.intuitive.com/en-us). After the introduction of the da Vinci platform in Italy in 1999, there were 111 robots active in our county in 2019; of those 22 placed in Lombardy region [19]. To use the robotic platform, specific training is required. Usually, it is provided by the manufacturer and distributor and is addressed to both the surgeon and all operating room personnel, also involving anesthesiologists and sterilization personnel [19]. In the area served by the ATS of Milan, the Training School in Robotic Surgery of the Department of Health Sciences of the State University of Milan was recently established. The robotic lung-thoracic surgery system comes alongside open surgery and video-assisted thoracoscopy (VATS). VATS is a minimally invasive approach that does not require classic thoracotomy. VATS instrumentation includes optics in addition to classic thoracic or laparoscopic instruments [20]. Minimally invasive surgery (both robotic and VATS) has several benefits over open

surgery, such as a lower risk of infection and a lower healing and recovery time, while maintaining overlapping efficacy outcomes [21]. Robotic surgery ensures a greater degree of flexibility compared to the laparoscopic approach, it allows to operate even in hard-to-reach locations, uses instrumentation with greater stability and allows a very precise three-dimensional view [2].

However, the cost of the necessary equipment is relevant; the purchase cost is about 1.7 million euros, while the annual maintenance represents about 10% of this sum. In addition, we have to add the costs

for disposable material and equipment with limited reusability (usually ten procedures). Consequently, the cost of this technology is high and volume dependent [4]. The European Society of Medical Oncology (EMSO) also highlights the fact that the robotic approach can be more expensive than the commonly used VATS [22]. On the other hand, in the robotic approach other costs are reduced, such as those related to hospitalization, the occupation of intensive care units, and the treatment of complications, which are reduced. Furthermore, there are potential advantages such as reduction of blood loss and tissue trauma, and less need for surgery conversion to open surgery compared to VATS. Furthermore, from the patient's point of view, there is an improvement in the quality of life (less pain, faster healing with consequent rapid return to work, less burden on caregivers). Lastly, this method has the advantage of improving ergonomics and reduce the physical effort of the surgeon [23]. Previous studies have attempted to evaluate the cost-effectiveness profile of this method in the thoracic area. Camberlin's study [4] is an HTA report carried out by the Belgian agency KCE, whose economic evaluation consists of a literature review for cost evaluation and a budget impact analysis. This study highlights that the cost structure of the different surgical approaches is very different and difficult to compare and the studies are generally of low quality. However, the analysis of the studies points out that robotic surgery is more expensive than traditional approaches such as thoracotomy and VATS. The systematic review by Turchetti [24] draws the same conclusion, while focusing on further relevant aspects: the facilitation in the execution of complex and advanced operations and the different role of the assistant surgeon during robot-assisted thoracoscopy operations. The organizational aspect most addressed in the literature was instead the training course for the use of the robotic surgical platform [19].

2. OBJECTIVE

2.1. PRIMARY OBJECTIVE

The objective of the analysis is to compare the cost-effectiveness profile of robotic surgery with that of thoracotomy and VATS in the surgical treatment of operable lung cancers in the adult population of the ATS of Milan.

2.2. SECONDARY OBJECTIVES

The secondary objective of the study is to compare the cost-effectiveness profile of robotic surgery versus that of thoracotomy and VATS in the surgical treatment of benign lung lesions in the same population.

3. METHODS

3.1. OVERALL DESIGN AND ORGANIZATION OF THE STUDY

Single multicenter retrospective observational study with Real World Evidence (RWE) approach [25], i.e. an evaluation that uses real-world data (RWD) derived from healthcare flows of the ATS of Milan and data provided by participating centers on the basis of medical records/ clinical databases, both as regards the analysis of efficacy and safety and as regards the economic evaluation of direct costs. For the analysis of quality of life and the calculation of QALYs (quality-adjusted life years), validated questionnaires will be prospectively administered to the participating subjects. The Epidemiology Unit of the ATS of Milan is the study promoter and it will coordinate the collection of data and will carry out the statistical and economic analyses. Other participating centers will be the

thoracic surgeries of the ATS hospitals, which carried out in 2019 (last pre-pandemic COVID-19 year) at least 50 lung operations with the ICD-9-CM codes shown in Table 1.

Table 1

ICD-9-CM code	Description		Description	
32.29	Other local excision or destruction of lesion or tissue of lung			
32.3	Segmental resection of lung			
32.4	Lobectomy of lung			
32.5	Pneumonectomy			

Both for the evaluation of clinical efficacy and of costs, the study will include all adult subjects (age equal or over 18 years of age at the time of surgery) residents in the ATS of Milan, who were hospitalized between 01/01/2016 and 31/12/2021 for pulmonary surgery (operation codes in any position of the hospital discharge summary form (SDO – Scheda di Dimissione Ospedaliera)) included in Table 1) and whose hospitalization is present in the SDO database of the ATS of Milan in one of the participating centers . For the evaluation of cost-effectiveness in malignant tumors, subjects with metastases at diagnosis will be excluded.

3.2. TECHNICAL CHARACTERISTICS OF ROBOTIC SURGERY, ORGANIZATIONAL AND ETHICAL ASPECTS OF THE TECHNOLOGY

The technical characteristics of the technology under evaluation will be summarized (ie type of device, procedure, etc.). A survey (**Annex 1**) will also be carried out at the participating centers to obtain indications on the temporal phases of acquisition of the technology in its subsequent developments in the territory under study. The organizational aspects will also be described, comparing them with those of the currently most widespread technologies according to the model proposed by Cacciatore et al. [26]. Finally, any problems of an ethical nature posed by the introduction of technology will be highlighted [27].

3.3. CLINICAL EFFECTIVENESS AND SAFETY

Within the evaluation of relative efficacy, we will evaluate clinical efficacy and safety, i.e. undesirable or harmful effects.

3.3.1. Design of the retrospective observational study for efficacy evaluation

For the group of patients who have undergone pulmonary surgery, extracted from the SDOs as described in paragraph 3.1, the surgical modality of each surgery will be identified starting from the administrative databases (ICD-9-CM codes 00.31-00.39 for robotic surgery and 34.21 for VATS in any location, Table 2). Given that preliminary assessments state a low sensitivity of these codes in identifying the surgical approach, this data will be supplemented by information relating to the surgical technique used and not contained in the SDO provided by the participating centers as reported in **Annex 2**.

Table 2 ICD-9-CM codes for the identification of interventions in VATS and robotic surgery

Surgery	Description	Code
VATS	Transpleural thoracoscopy	34.21
Robotics	Computer assisted surgery with CT/CTA	00.31
	Computer assisted surgery with MR/MRA	00.32
	Computer assisted surgery with fluoroscopy	00.33

Imageless computer assisted surgery	00.34
Computer assisted surgery with multiple datasets	00.35
Other computer assisted surgery	00.39

Following preliminary descriptive analyzes on these data, we will evaluate in which types of surgery, among those listed in Table 1, the three surgical methods under analysis are actually used (thoracotomy, video-assisted thoracoscopy (VATS) and robotic surgery). If open surgery is used, the approach will be further evaluated (i.e.posterolateral, muscle-sparing lateral, axillary or anterolateral, thoracosternotomy, or median sternotomy [28]. Instead, in case VATS method is used [29], it will be assessed whether a single surgical access technique (Uniportal VATS) [30], double access (Duke's approach) [31] or triple access (Copenhagen's approach) [32] was used. Furthermore, for ATS residents who underwent surgery a distinction will be made on the operations preceded by histological examination confirmatory of malignancy, comparing the date and the basis of diagnosis of the ATS cancer registry, from those performed for benign tumors and lesions with uncertain malignant potential.

3.3.2. Prospective study design for the evaluation of quality of life and efficacy

All subjects who will undergo lung surgery (Table 1) during 2022 at the participating centers and will give their consent to participate in the study by signing the informed consent form at the prehospitalization or at hospitalization before surgery will be eligible to be enrolled. To evaluate the quality of life PROMs related, we will use the generic questionnaire EuroQol-5 Dimension (EQ-5D-5L) and the specific European Organization for Research and Treatment of Cancer Quality of Life Questionnaire-Lung Cancer (EORCT QLQ-LC29), which are available and validated in Italian [33,34]. The pre-intervention questionnaire will be completed on paper during hospitalization before the intervention or at pre-admission and the data will be entered into the web application of the ATS of Milan by dedicated staff. The subsequent questionnaires at day 7 and 30 can be self-completed by patients or electronically, using the dedicated web application of the ATS of Milan or in paper form, by filling in the documents issued on discharge for this purpose. At the first follow-up visit after 30 days, the patient will deliver the completed forms to the Thoracic Surgery department in charge of him. The Thoracic Surgery Department will forward all the documents, including pre-intervention documents, in a single mailing at the end of the study, to the Epidemiology Unit of ATS of Milan. The latter will enter the data and prepare it for subsequent analyses. The choice of how to complete the questionnaire will be left to the participating center. In both cases, when completing the first questionnaire, the study staff will enter the patient's fiscal code (patient identifier) in the application and a unique random ID will be generated which will be issued to the patient on paper so that he can enter it in the two subsequent self-compiled questionnaires. The information necessary for the evaluation of efficacy will be collected with the same modalities of the retrospective study. In addition to the evaluation of the quality of life, a questionnaire for the collection of patient experience (PREMs) will also be administered 30 days after the intervention or at the first follow-up visit [35,36]. The PREMs questionnaire will also be self-completed by patients either electronically, using the dedicated web application of the ATS of Milan, or in paper form, by filling in the document issued during hospitalization, the transmission of which to the Epidemiology Unit will take place with the methods indicated above.

Definition of efficacy outcomes

Efficacy and safety will be evaluated starting from the diagnosis and procedure fields of the SDO, from the life status derived from the ATS patient registry (NAR – Nuova Anagrafe Regionale) and from the data provided by the centers in terms of:

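### At paper centres the day-7 quality-of-life form is handed over only at discharge, so patients still in hospital on day 7 risk missing or late data, plausibly more often after open surgery

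*Combined protocol and SAP*

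**What the plan says.** Section 3.3.2 plans a questionnaire before surgery and two afterwards: "The subsequent questionnaires at day 7 and 30 can be self-completed by patients or electronically". Two routes are offered, "using the dedicated web application of the ATS of Milan or in paper form", and the paper route is defined as "in paper form, by filling in the documents issued on discharge for this purpose". On the route itself: "The choice of how to complete the questionnaire will be left to the participating center".

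The patient identifier does not wait for discharge. At the first, pre-operative questionnaire "a unique random ID will be generated which will be issued to the patient on paper". Paper forms come back late: "At the first follow-up visit after 30 days, the patient will deliver the completed forms to the Thoracic Surgery department", and the department then sends everything to the coordinating unit in one mailing at the end of the study.

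The same section treats the patient-experience (PREMs) paper form differently. That one is completed "by filling in the document issued during hospitalization".

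Section 3.3.4.3 compares the utility index between approaches with a longitudinal model weighted by the inverse probability of surgical approach. It names no completion window and no rule for late or missing questionnaires. Section 3.4.3 takes the QALY utilities from the same EQ-5D answers.

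**The concern.** At a paper centre that follows the text, a patient who is still an inpatient seven days after surgery does not hold the day-7 form. That patient will skip it, fill it in late, or answer from memory. The documents describe no ward completion. Because forms are returned only after day 30, nobody would notice in time to correct it.

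The loss is unlikely to fall evenly. Section 1 credits minimally invasive surgery with "a lower risk of infection and a lower healing and recovery time" relative to open surgery and says that the robotic approach lowers hospitalisation costs. Section 3.3.2.2 makes duration of hospitalisation a compared quantity. Being an inpatient on day 7 is therefore expected to depend on approach and on how well the patient is recovering. Weights built from the probability of receiving each approach deal with confounding before surgery. They do not deal with absence or mistiming that depends on recovery afterwards.

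At stake is the day-7 comparison of utility, one of only two post-operative assessments. If the absent patients are the less well ones, open surgery looks better at day 7 than it was, and the advantage of the other approaches shrinks.

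**Working it through.** **1. Stated power reproduced.** Section 3.3.4.1 gives groups of 48 robotic, 94 VATS and 258 open, SD 17.2, a week-4 VAS mean of 73.5 for open and 78.1 for VATS, and 80 to 83 assumed for robotic. Alpha is not stated for this calculation; I assume two-sided 0.05. For robotic versus open:

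- Standard error = 17.2 × √(1/48 + 1/258) = 2.704.
- Noncentrality at a robotic mean of 80 = 6.5 / 2.704 = 2.404; error df = 400 − 3 = 397.
- Noncentral-t power for means of 80, 81, 82 and 83: 0.669, 0.790, 0.880, 0.939.

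This matches the plan's table exactly. The table concerns week 4, so the day-7 form does not alter it.

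**2. Lost precision alone is small.** Borrowing the week-4 inputs for day 7, as illustration only, and removing open patients:

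| Open forms missing | Power, robotic mean 80 | Power, robotic mean 83 |
|---|---|---|
| 0% | 0.669 | 0.939 |
| 20% | 0.652 | 0.930 |
| 50% | 0.605 | 0.902 |

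**3. How many patients.** The documents give neither length of stay nor the share of patients at paper centres (p). Assume 20–50% of open, 10–25% of VATS and 10–20% of robotic patients are inpatients on day 7. Patients without an on-time form = group size × share × p.

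| Group | p = 1 (all centres on paper) | p = 0.5 |
|---|---|---|
| Open, 258 | 52–129 | 26–65 |
| VATS, 94 | 9–24 | 5–12 |
| Robotic, 48 | 5–10 | 2–5 |

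**4. Selection.** If a share q of a group is missing and its mean lies D points below those observed, the true mean is (1 − q) × observed + q × (observed − D) = observed − qD. The observed mean is therefore too high by qD, and the VATS-minus-open difference is understated by p × (q_open − q_VATS) × D. Take D = 8.6, half of the SD of 17.2, as an assumption:

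- q = 20% open, 10% VATS: 0.10 × 8.6 = 0.86 points at p = 1; 0.43 at p = 0.5.
- q = 50% open, 25% VATS: 0.25 × 8.6 = 2.15 points at p = 1; 1.08 at p = 0.5.

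The planned week-4 VATS–open difference is 78.1 − 73.5 = 4.6 points, used here only as a yardstick. These figures treat forms as missing. Late forms entered as day 7 would distort the contrast in a way that cannot be signed or sized from the documents.

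**5. Weight in the QALY.** With linear interpolation between days 0, 7 and 30 (my assumption), the day-7 value carries 7/2 + 23/2 = 15 days. The horizon in section 3.4.2 is 5 years, about 1,826 days, so that is 15/1,826 = 0.8%. A utility error of 0.10 at day 7 moves the QALY by 0.10 × 15/365.25 = 0.004.

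**6. The origin of day 7.** Section 3.3.2 does not name it. Surgery is the natural reading, because the PREMs questionnaire in the same section is timed from the intervention. If discharge were meant, everyone would hold the form, but a patient discharged L days after surgery would answer on day L + 7. Time since surgery would then vary with stay, and so plausibly with approach.

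**The case against.** The strongest reply is that this is a conditional risk. It needs the centre to choose paper, day 7 to run from surgery, a material share of stays beyond seven days, a difference in that share between approaches, and staff who apply the discharge wording literally. The web route is not tied to discharge, and the identifier is issued before surgery, so an inpatient at a web centre can answer on time. The sentence describing the routes is loosely worded, and Annex 3, the collection form, is listed but not available here; it may carry a completion date.

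Most of this stands as a limit on size. It does not remove the point. A date field would show that a form was late but would not put it in an inpatient's hands. If day 7 runs from discharge, one problem replaces another. Treatment centre is a candidate variable for the weights, but that cannot address differences in stay within a paper centre. A likelihood-based longitudinal model could recover part of the loss from baseline and day-30 answers; section 3.3.4.3 does not name the model, and this would not help with late answers labelled day 7.

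A reader might infer more: that the missing patients are mostly open-surgery patients, that the comparison is biased, or that the cost-utility result is in doubt. The documents do not support these. They contain no length-of-stay figure; section 1 speaks of recovery and of hospitalisation costs, not days. Open surgery is 258 of the 400 expected patients, which makes it the largest group but says nothing about its rate of long stays. Losses in the other groups offset part of any bias. The QALY weight of day 7 is under 1%.

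**Conclusion.** The point holds as a risk confined to centres that choose paper. The stated hand-over rule, if followed, leaves day-7 inpatients without a form, and nothing else in the plan compensates. Data are plausibly missing or late more often after open surgery and in slower recoverers, which would tend to flatter open surgery if forms are missing rather than late.

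The size cannot be established from the documents. Under assumed inpatient shares, a half-SD deficit and half or all of the patients at paper centres, the day-7 VATS-versus-open contrast is understated by about 0.4 to 2.2 VAS points. The effect falls on the day-7 utility comparison and the descriptive pre- and post-operative comparisons. It is negligible for the 5-year QALY and nil for the stated week-4 power. Day 30 is affected only for a patient still in hospital then, provided it too counts from surgery. The change is worth making because it is nearly free.

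**What to change.** In section 3.3.2:

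- State that day 7 and day 30 count from the date of surgery.
- Hand out both paper forms with the baseline questionnaire and the paper identifier, or during hospitalisation as is already planned for PREMs.
- State that a patient still in hospital on day 7 completes the form unaided on the ward.
- Record the completion date on every form, if Annex 3 does not already do so.

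In section 3.3.4.3, use the actual number of days from surgery to completion in the longitudinal model instead of the nominal day.

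The cost is a small change in form logistics: the same forms given out earlier and one date to enter. No staff or visits are added. Forms issued before surgery may be mislaid during the stay; handing them out on the ward after surgery and before day 7 avoids most of that.
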